1.4. Clinical Data to date

The *QuikClot® Radial®* pad has received FDA clearance for use in local management of bleeding wounds such as vascular access sites. It provides an alternative to other hemostatic devices and could potentially reduce

OFFICE OF HUMAN RESEARCH

hemostatic time, reduce vascular complications and shorten time in hospital stay. By PubMed search with key words including *QuikClot® Radial®* pad, vascular access, hemostatic devices, and hemostasis showing the available clinical data to date regarding use of the *QuikClot® Radial®* pad as following:

Additional Clinical Data/References:

Several peer reviewed clinical publications support the use of QuikClot Interventional Hemostatic Bandage in human patients on drug/induced anticoagulant therapy.

TABLE 2

Study Name/Description	Trabattoni D, et al. A New Kaolin-based Hemostatic Bandage Use after Percutaneous Coronary Diagnostic and Interventional Procedures; Internat J Cardiol; 2010 Nov 172.														
Number of sites/investigators (OUS/US)	One site (OUS). Three investigators														
Number of subjects	40 subjects														
Inclusion/	Patients undergoing diagnostic angiography or percutaneous coronary intervention via a femoral artery approach														
Exclusion	Not described in publication														
Procedure	Prospective single arm pilot trial of QuikClot Interventional Hemostatic Bandage in cardiac catheterization. Introducer sheath size 6 Fr (90%) or 7 Fr (10%) Femoral artery sheath removed once the ACT < 180 seconds All patients were treated with QuikClot Interventional Hemostatic bandage after arterial sheath removal														
Study endpoints and assessment protocol	Complete 100% bleeding cessation at 5 minutes and safe ambulation at 4 hours														
Duration of follow-up	30 days														
Patient Demographics	75% male Mean Age = 68+/- 11 years														
Patient condition (means of achieving anticoagulation, level of anticoagulation)	Patient undergoing diagnostic angiogram (62%) vs. Percutaneous Coronary Intervention PCI (38%) via femoral artery approach 6F (90%) 7F (10%). 
  
 	QuikClot n=40	
   
 LMW Heparin	2.5%	
 
 Aspirin + Clopidogrel	27.5%	
 
 Aspirin	60%	
 
 Aspirin + Warfarin	5%	
 
 IV Heparin	38%	
 
 No anticoagulation	5%	
  
		QuikClot n=40	LMW Heparin	2.5%	Aspirin + Clopidogrel	27.5%	Aspirin	60%	Aspirin + Warfarin	5%	IV Heparin	38%	No anticoagulation	5%
	QuikClot n=40														
LMW Heparin	2.5%														
Aspirin + Clopidogrel	27.5%														
Aspirin	60%														
Aspirin + Warfarin	5%														
IV Heparin	38%														
No anticoagulation	5%														
Study results	Mean ACT value at hemostasis 138 + 24 seconds (range 95-186 seconds) Mean cumulative hemostasis time 4.9 ± 1.05 min 
 Diagnostic procedures 4.2 ± 0.9 min Interventional procedures 5.3 ± 0.95 min Ambulation time 4 h for all patients														
Adverse events	One PCI patient required extra compression time to achieve hemostasis and developed a small (< 5cm) hematoma														

TABLE 3

Study Name/Description	Trabattoni D, et al. A New Kaolin-based Haemostatic Bandage Compared with Manual Compression for Bleeding Control after Percutaneous Coronary Procedures; Eur Radiol, 2011 Aug 21(8): 1687-91.																						
Number of sites/investigators (OUS/US)	One site (OUS), six investigators																						
Number of subjects	200 subjects Prospective randomized trial of QuikClot(n=100) vs. manual compression (n=100)																						
Inclusion/	Undergoing angiography or percutaneous coronary intervention via a femoral approach																						
Exclusion	Patients with baseline INR > 1.4 excluded Patients who had previous arterial access at the same femoral site within 30 days excluded																						
Procedure	Femoral arterial sheath removed once the ACT \leq 180 seconds Patients randomized to receive QCI gauze or manual compression after femoral sheath removal Patient ambulation at 4 hours.																						
Study endpoints and assessment protocol	Complete 100% bleeding cessation at 5 minutes and safe ambulation at 4 hours																						
Duration of follow-up	30 days																						
Patient demographics	Male 70% QuikClot vs. 60% Control Mean age (years) 65.7 ± 13 vs. 73.6 ± 6.2 Weight (Kg) 73.9 ± 12 vs. 71.2 ± 15 Diagnostic procedure (n=98) vs. Percutaneous coronary intervention (n=102) Introducer sheath size 6 Fr (90%) or 7 Fr (10%)																						
Patient condition (means of achieving anticoagulation, level of anticoagulation)	
  
 	QuikClot	Control	
   
 LMW Heparin	4%	2%	
 
 Aspirin + Clopidogrel	29%	26%	
 
 Aspirin	60%	60%	
 
 Aspirin + Warfarin	7%	3%	
 
 IV Heparin	51%	49%	
 
 No anticoagulation	0%	9%	
  
			QuikClot	Control	LMW Heparin	4%	2%	Aspirin + Clopidogrel	29%	26%	Aspirin	60%	60%	Aspirin + Warfarin	7%	3%	IV Heparin	51%	49%	No anticoagulation	0%	9%
	QuikClot	Control																					
LMW Heparin	4%	2%																					
Aspirin + Clopidogrel	29%	26%																					
Aspirin	60%	60%																					
Aspirin + Warfarin	7%	3%																					
IV Heparin	51%	49%																					
No anticoagulation	0%	9%																					
Study results	Mean ACT value at hemostasis 146 + 24 seconds (range 98 – 198 seconds) Hemostasis with QCI bandage = 5.4 ± 1.5 min Hemostasis with manual compression = 25 ± 15 min $p < 0.001$ No hemostasis failure in either group																						
Adverse events	Major Bleeding: 1 patient in each group Haematoma, > 5 cm 1* pt (QuikClot) vs. 2 pts (control) Pseudoaneurysm 1* pt (QuikClot) vs. 1 pt (control) *Same patient																						

TABLE 4

Study Name/Description	Politi L, et al. Randomized Clinical Trial on Short-Time Compression with Kaolin Filled Pad: A New Strategy to Avoid Early Bleeding and Subacute Radial Artery Occlusion after Percutaneous Coronary Intervention; J Internat Card; 2011; Vol 24; 65-72			
Objective	To evaluate the occurrence of 24 hour radial artery occlusion and the rate of bleeding of a novel hemostatic device for radial closure after percutaneous interventions, in adjunct to short-time compression.			
Number of sites/investigators (OUS/US)	One site (OUS). Ten investigators			
Number of subjects	120 subjects divided in 3 groups: Group 1 (QuikClot n=50) Group 2 (control short time – 15 minute compression n=20) Group 3 (control 2 hours compression time n=50)			
Inclusion/	All patients undergoing transradial elective diagnostic or interventional coronary procedures between November 1, 2009 and January 31, 2010			
Exclusion	Abnormal Allen's test before puncture Failure to provide written informed consent			
Procedure	QuikClot was applied to the radial artery over the sheath which was then removed. Pressure was maintained for 15 minutes and then completely relaxed.			
Study endpoints and assessment protocol	The main end-point was subacute Radial Artery Occlusion (RAO) The secondary end-point was failure of the closure technique (death, MI or major bleeding occurring in hospital) Groups 1 and 2: 15 minute assessment for bleeding Group 3: 2 hour assessment for bleeding All groups: Radial artery patency assessed at 24 hours using Barbeau's Test			
Duration of follow-up	Until patient discharge and follow-up visit. Follow-up at 6 months was done for patients who developed RAO			
Patient demographics	Age (years) Group 1 – 64.16 ± 11.53, Group 2 – 61.30 ± 14.22, Group 3 = 59.72 ± 14.23 (p=N/S) Male 37 (74%), 14 (70%), 36 (72%) (p=N/S) Weight (kg) 76.42 ± 11.13, 80.00 ± 14.96, 82.02 ± 13.26 (p=N/S)			
Patient condition (means of achieving anticoagulation, level of anticoagulation)		QuikClot	Control Group 1	Control Group 2
	Aspirin	46 (92%)	19 (95%)	50 (100%)
	Clopidogrel	10 (20%)	2 (10%)	11 (22%)
	LMW Heparin	8 (16%)	5 (25%)	5 (10%)
	Warfarin	6 (12%)	5 (25%)	5 (10%)
	IV heparin	100%	100%	100%
	No anticoagulation	0%	0%	0%
	Several patients received multiple therapies			
Randomization Assignment	Based on computer generated randomization list patient received one of the three treatment groups below: Group 1: Compression of radial artery using QuikClot Interventional hemostatic pad with folded gauze over the pad and taped for 15 minutes; Compression dressing then removed			

A previous study showed that after removal of 15 minutes of compression with the *QuikClot® Interventional™* pad, active bleeding occurred in 20% of patients, compared to 90% with 15 minutes of manual compression only after percutaneously accessed femoral arteries.¹⁶

Our pilot study in 30 patients undergoing TRA demonstrated that application of the *QuikClot® Radial®* pad with 5 minutes of manual compression followed by a light compressive elastic bandage supplied by Z-Medica LLC for 25 minutes or 55 minutes achieved 100% hemostasis following TRA, with no increased complications noted (see Table below).¹⁵

Post-procedure outcomes with the use of QuikClot® Radial® pad

	TR Band® (n = 10)	QuikClot® 30 min. (n = 10)	QuikClot® 60 min. (n = 10)	P Value
Compression time (min)	149.4 ± 36.5	30.7 ± 2.2	60.9 ± 2.9	< 0.001
Initial hemostasis	5 (50%)	10 (100%)	10 (100%)	< 0.001
Pain scale	0	0	0	NS
Recovery unit time (min)	263.3 ± 56.3	238.9 ± 114.8	237.6 ± 71.6	NS
Access-site complications				
Radial artery occlusion	0 (%)	0 (0%)	0 (0%)	NS
Hematoma	0 (0%)	1 (10%)	0 (0%)	NS
Ecchymosis	0 (%)	0 (0%)	1 (10%)	NS
Edema	0 (%)	0 (0%)	0 (0%)	NS
Rebleeding	0 (%)	0 (0%)	0 (0%)	NS
Other	0 (0%)	0 (0%)	0 (0%)	NS

Results are mean ± standard deviation or n (%); NS, Not significant

Our recent other preliminary study (data not yet published) further demonstrated that application of the *QuikClot® Radial®* pad with 5 minutes of initial manual compression following by 25 minutes of light compression with either a Coban™ bandage or Tegaderm™ dressing was successful in all 20 patients who underwent diagnostic cardiac catheterization and/or PCI, with 100% hemostasis without rebleeding, RAO, and other complications. This preliminary clinical evaluation suggests that the *QuikClot® Radial®* pad combined with either a Coban™ bandage or Tegaderm™ dressing is an easy to use and an effective hemostatic dressing that allowed for a short duration of compression and a painless hemostasis procedure. Thus, there is a need to assess the true efficacy and safety of the *QuikClot® Radial®* pad combined with either a Coban™ bandage or Tegaderm™ dressing in the management of radial hemostasis following TRA in a larger number of patients.

1.5. Dose Rationale and Risk/Benefits

The use of *QuikClot® Radial®* pad has been reported in patients undergoing percutaneous radial procedures, and the results demonstrated that application of the *QuikClot® Radial®* pad with short-term (15 minutes) radial compression had 20% rebleeding at the radial access site.¹⁶ Our recent preliminary results demonstrated that application of the *QuikClot® Radial®* pad with 5 minutes of initial manual compression following by 25 minutes of light compression with either a Coban™ bandage or Tegaderm™ dressing was successful in all 20 patients who underwent diagnostic

cardiac catheterization and/or PCI, with 100% hemostasis without rebleeding, RAO, and other complications (unpublished data). We therefore chose these same compression times for this proposed larger study.

After an interim analysis of 186 subjects, with a failure to obtain initial hemostasis at 5 minutes in approximately 30% of the subjects in the Tegaderm™ only arm of the protocol, we believed there would be little chance of this Tegaderm™ only protocol being adopted clinically. Our DSMB committee reviewed the results and recommended to stop the Tegaderm™ only arm in the prior protocol. There were no safety issues with the Tegaderm™ only arm, as with repeated manual compression cycles of the QuikClot® pad, hemostasis was obtained in all subjects. There was just clinical futility of this arm of the protocol as written that was not detected in the small pilot trial performed using this protocol. A new arm 3 will replace the old Tegaderm™ only arm in this present revised protocol. This new arm 3 will use a QuikClot® pad under a TR Band® with 30 minutes of compression. We have a large successful anecdotal experience of using a QuikClot® pad under a TR Band® with 30 minutes of compression. Other hemostatic pads have been successfully used under a TR Band® [17, 18]. As we have a large anecdotal successful experience of 30 minutes of compression with QuikClot® Radial and QuikClot Interventional Pads under a TR Band®, we choose a compression time of 30 minutes for the QuikClot®/TR Band® arm.

Although the TR Band® radial compression device has been used for years as the standard of care for hemostasis after TRA, there is no “standardized” compression/weaning technique. In a previous study, we used 40 minutes of compression with the TR Band® and then began weaning. 50% of subjects had to have air re-inflated upon the initial weaning of the TR Band®.¹⁵ Carrington reported that a 1-hour commencement of TR Band® weaning following TRA appears to be safe, with an 84% success rate.¹⁹ Because of this, the TR Band® in this study will be inflated for 60 minutes of compression without weaning, and then weaned over the next 60 minutes to hopefully achieve a high rate of hemostasis with a low rate RAO.

Potential risks may include: bleeding, pseudoaneurysm formation, hematoma, radial artery occlusion, local skin reaction (redness, swelling, and rash), pain, and numbness. Subjects may or may not have some or all of these risks from treatment with either one of the devices used in this study. The risks for the use of the *QuikClot® Radial®* pad are the same as for standard of care with TR Band®.

There may be an immediate potential benefit to patients. Application of the *QuikClot® Radial®* pad may shorten the time of compression compared with the standard of care TR Band®. Shorter radial artery compression times have been associated with less radial artery occlusion, thus potentially reducing the incidence of post-procedural radial artery occlusion. The light compression with either a Coban™ may help maintain patent hemostasis. Patient discomfort may also be reduced by shorter compression times and lower compression pressure.

1.6. Anticoagulation

For diagnostic cardiac catheterization using TRA in this study, a heparin dose of 70 units/kg will be used, with a minimum of 4000 units and a maximum of 7000 units. For PCI, additional heparin to attain an ACT of > 250 – 300 seconds will be used, or bivalirudin at standard FDA approved doses described in the package insert may be used at the operator’s discretion. The option of continuing a heparin or bivalirudin infusion after the PCI will be at the operator’s discretion.

2. Study Objectives

The objective of this study is to evaluate the safety and efficacy of a kaolin-based *QuikClot® Radial®* pad combined

with either a Coban™ bandage or TR Band® to achieve hemostasis after TRA, compared with ‘standard of care’ mechanical compression with the TR Band®, with the aim to hopefully develop a safe and possibly superior hemostatic method after transradial access, thus improving patient care by optimizing radial hemostasis management.

3. Study Design

[figure not shown]
3.1. General Design

The SPIRIT (Standard Protocol Items for randomized Trials) recommendations were followed in preparing the protocol.^{20, 21} The study is a single center, prospective, randomized, controlled trial with three arms (below) to compare hemostasis times and potential complications after TRA in patients undergoing diagnostic cardiac catheterizations and/or PCI.

Arms	Assigned Interventions
TR Band®: Hemostasis will be achieved by TR Band® after the transradial procedure. TR Band® will be applied over the arteriotomy site for 60 minutes and weaned over the next 60 minutes.	Device: TR Band®, Terumo
QuikClot® Radial® pad + Coban™: Hemostasis will be achieved by the QuikClot® Radial® pad secured with a Coban™ after the transradial procedure. 5 minutes of initial manual compression will be applied on the QuikClot® Radial® pad/Coban™ bandage, followed by 25 minutes of light compression with the Coban® bandage only. The Coban™ bandage is then removed, and a Tegaderm™ dressing is applied over the QuikClot® Radial® pad, to be removed the following morning.	Device: QuikClot® Radial® pad, Z-Medica, LLC. Coban™, 3M
QuikClot® Radial® pad + TR Band®: Hemostasis will be achieved by the QuikClot® Radial® pad with a TR Band® inflated with 8-10 cc of air after the transradial procedure. The QuikClot® Radial® pad is placed over the access site and covered by a Tegaderm™ dressing, then a TR Band® will be applied over the QuikClot® Radial® pad/Tegaderm™ for 30 minutes, then deflated within 1 minutes, followed by the Tegaderm™ dressing covering the QuikClot® pad until the following morning.	Device: QuikClot® Radial® pad, Z-Medica, LLC. Tegaderm™, 3M

Up to now, 217 subjects have been enrolled in this trial per the previous version of this protocol, including 73 in the QuikClot®/Tegaderm™ arm, 72 in the TR Band® only arm, and 72 in the QuikClot®/Coban™ arm. This amended protocol will continue enrolling a total of 100 subjects for both the TR Band® only and the QuikClot®/Coban™ arms, respectively. The new arm 3, QuikClot®/TR Band®, will also enroll a total of 100 subjects. In this amended protocol, a total of 373 subjects will be enrolled, including the 217 that have been enrolled in the prior version of the protocol, and an additional 156 subjects enrolled in this amended protocol. Randomization of the 156 subjects in the amended protocol will continue into the 3 cohorts. As 100 subjects will be needed to fill the new Arm 3, QuikClot®/TR Band®, and only 28 subjects will be needed to fill each of Arms 1 and 2, i.e. the TR Band® and QuikClot®/Coban™ Arms, arms 1 and 2 will fill well before the new Arm 3. After Arms 1 and 2 are filled, participants assigned to Arms 1 and 2 will be considered screen failures. All screen failures in this revised protocol will be assigned into the new Arm 3, the QuikClot®/TR Band® arm. As the old arm 3 is terminated, future participants randomized into arm 3 will be considered screen failures, as our REDCap data base will consider them in the old Arm 3. All screen failures that occur during randomization in the additional 156 subjects in this revised protocol will be assigned to the new Arm 3. An example of this would be a subject randomized to Arm 1 (TR Band®) who is a diagnostic cath only, and the 50 diagnostic only cases in Arm 1 are already filled. This subject would then be assigned to new Arm 3, the QuikClot®/TR Band® arm. Another example would be a participant randomized to Arm 3. As the old Arm 3 from the prior protocol is now closed, any

subsequent participants randomized to Arm 3 will be considered screen failures, and will be assigned to the new Arm 3 of this revised protocol. Each arm of 100 patients will include 50 diagnostic-only cardiac catheterizations and 50 PCIs. Simultaneous accrual of diagnostic-only cardiac caths and PCIs will occur.

- For the TR Band®, weaning begins at the end of 60 minutes of compression and will complete over the next 60 minutes. If oozing/bleeding occurs at any point during the weaning of air, reinflation and repeat weaning will be performed per protocol.
- For the QuikClot® Radial® pad/Coban™ cohort, firm manual pressure will be released after 5 minutes. If oozing/bleeding occurs after the release of manual pressure, repeat manual pressure will again be applied over the QuikClot® Radial® pad secured by a Coban™ per protocol.
- For the QuikClot® Radial® pad/TR Band® cohort, the QuikClot® Radial® pad will be secured with a TR band® inflated with 8-10 cc of air for 30 minutes, weaning begins at the end of 30 minutes of compression and will complete within 1 minute. If oozing/bleeding occurs after the weaning, reinflation and repeat weaning will be performed per protocol.

Scheme 1. Proposed workflow for two compression devices: *QuikClot® Radial®* pad and TR Band®

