Study Product, Dose, Route, Regimen	The QuikClot® Radial® pad will be applied over the radial artery access site covered with either a Coban™ bandage or a TR Band® after TRA. Firm manual compression will then be applied over the QuikClot® Radial® pad after the sheath is removed for 5 minutes in the Coban™ cohort. The Coban™ cohort will then have the Coban™ bandage removed after an additional 25 minutes, then being covered with a Tegaderm™ dressing. In the QuikClot® Radial® pad combined with a TR Band® cohort, the radial sheath is removed and the TR Band® is inflated with 8 – 10 mL of air after a small amount of blood is noted on the QuikClot® Radial® pad. After 30 minutes the TR Band® is removed, leaving the QuikClot® pad covered with the Tegaderm™ dressing over the skin entrance site, to be removed the following morning.
Assigned Interventions	Consented subjects will be randomly assigned in the cardiac cath lab upon completion of their procedure into the following three arms: Arm 1 – Standard of Care with a TR Band® Arm 2 – QuikClot® Radial® pad combined with a Coban™ bandage Arm 3- QuikClot® Radial® pad combined with a TR Band®
Reference therapy	TR Band®

Table of Contents

1. Introduction	1
1.1 Background	1
1.2. Summarized Details of Investigational Products	2
1.2.1. Device Description	2
1.2.2. Intended Use	3
1.2.3. Technological Characteristics and Substantial Equivalence	3
1.3. Device Usage	3
1.4. Clinical Data to date	6
1.5. Dose Rationale and Risk/Benefits	10
1.6. Anticoagulation	11
2. Study Objectives	11
3. Study Design	11
3.1. General Design	11
3.2. Primary Study Endpoints	13
3.3. Secondary Study Endpoint	13
4. Subject Selection and Withdrawal	14
4.1. Inclusion Criteria	14
4.2. Exclusion Criteria	14
4.3. Subject Recruitment and Screening	15
4.4. Method for Assigning Subjects to Treatment Groups	15
4.5. Compliance Monitoring	15
5. Study Procedures	15
5.1. Visit 1 –At time of Standard of Care Cardiac Catheterization and/or PCI	15
5.2. Visit 2 – One day after enrollment	16
6. Safety and Adverse Events	16
6.1. Definitions	16
6.2. Adverse Event Reporting Period	17
6.3. Recording of Adverse Events	17
6.4. Reporting of Serious Adverse Events	17

7. Data Handling and Record Keeping.....	17
7.1. Confidentiality	17
7.2. Data Management.....	18
7.3. Sample Size and Statistics	18
7.4. Dissemination Plan.....	18
8. Ethical Considerations.....	18
9. References.....	19
10. Lists of abbreviations.....	21

1. Introduction

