1.3. Device Usage

Application of the *QuikClot® Radial®* pad will be performed by properly trained interventional cardiologists.

Application of the TR Band® will be performed by properly trained interventional cardiologists or cath lab technicians. Proper training for physicians for either device is defined as performing 2 run in procedures prior to enrolling patients in this study, supervised by a cardiologist or industry representative experienced with the either device. For cath lab technicians, proper training will be meeting the qualifications outlined by the Memorial Cardiac and Vascular Institute cath lab protocol for application of the TR Band®. [name], [name] and [name] are properly trained with the use of the *QuikClot® Radial®* pad hemostatic device and TR Band®.

1.3.1. The method for using the *QuikClot® Radial®* pad with a Coban™ Self-Adherent Wrap is as follows:

After an end-procedure ACT is drawn and the blood pressure is recorded, the arterial access sheath will be partially pulled out of the radial artery, exposing approximately 4 cm of sheath. The level of the access site will be marked on the medial and/or lateral side of the palmar surface of the wrist with a sterile marker pen so that once the pad is applied and covering the access site, the investigator will still be able to know the exact level of the access site, to properly hold pressure in the correct spot. (Fig.4A, Arrows). The *QuikClot® Radial®* pad is then applied over the access site, with the sheath still in place, with 1/3 of the pad being distal to the access site and 2/3 of the pad being proximal to the access site (Fig.4B, Arrows). The 3M™ Coban™ latex-free self-adherent wrap is then gently applied, wrapping 3-5 layers around the wrist to hold the *QuikClot® Radial®* pad in place (Fig. 4. C). When application is complete, the excess self-adherent wrap will be cut off (Fig. 4D). The 3 – 5 layers will then be hand massaged to allow the layers to adhere to each other (Fig. 4E). The sheath is then removed from the radial artery,

Fig 1. Application of the QuikClot® Radial® pad with the Coban™.

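### New Arm 3 v TR Band is planned as a randomised 100 v 100 comparison, but 72 of the 100 controls predate Arm 3 and, under a 1:1:1 list, about 70 of the 100 Arm 3 subjects had no randomised chance of TR Band

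*Combined protocol and SAP*

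**What the plan says.** The Study Summary says "Consented subjects will be randomly assigned in the cardiac cath lab upon completion of their procedure into the following three arms", and section 3.1 describes a "prospective, randomized, controlled trial with three arms (below) to compare hemostasis times and potential complications after TRA". Section 7.3 sizes each QuikClot arm against TR Band at 100 per arm, and new Arm 3 takes over the figure of 100 from the closed Tegaderm arm.

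Section 3.1 also sets out how the arms will fill. Before the amendment 217 subjects were enrolled, including "72 in the TR Band® only arm". TR Band and Coban each need 28 more and Arm 3 needs 100. The protocol expects that "arms 1 and 2 will fill well before the new Arm 3". Its solution is a redirect: "After Arms 1 and 2 are filled, participants assigned to Arms 1 and 2 will be considered screen failures", and "All screen failures in this revised protocol will be assigned into the new Arm 3". This covers every draw to the old Arm 3 slot and every draw to a full Arm 1 or 2. It works by procedure type as well as overall. The protocol's example is a diagnostic-only subject drawn to TR Band when "the 50 diagnostic only cases in Arm 1 are already filled", who is moved to Arm 3. Section 4.4 confirms that the existing REDCap allocation continues.

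The analysis text in section 7.3 plans a t-test at a two-sided 0.05. It mentions no concurrent controls, enrolment period, or restriction to subjects who could have been drawn to either arm.

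**The concern.** A randomised comparison of Arm 3 with TR Band needs subjects who could have received either at the time they were assigned. Two groups do not qualify: TR Band subjects enrolled before Arm 3 existed, and Arm 3 subjects who entered when TR Band was already full for their procedure type. For the second group every possible draw leads to Arm 3.

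If these groups are pooled and reported as randomised, any difference between periods in case mix, operator experience or practice is counted as a device effect, in either direction. The endpoints exposed are initial successful hemostasis (section 3.2.1), on which the sample size rests, and radial artery occlusion (section 3.3.1).

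**Working it through.** **Plan's own counts (section 3.1).** 73 + 72 + 72 = 217 enrolled. 100 − 72 = 28 places left in each of Arms 1 and 2. 28 + 28 + 100 = 156 further subjects, and 217 + 156 = 373. These reproduce. The 72 of 100 early controls is exact and needs no assumption.

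**Arm 3 subjects with no randomised chance of TR Band.** Section 4.4 gives neither the ratio nor the block size. I assume 1:1:1, which fits 73/72/72 enrolled and equal targets. With simple randomisation and no procedure-type caps:
- Subjects needed to draw TR Band 28 times: 28 ÷ (1/3) = 84 on average.
- Subjects left: 156 − 84 = 72. On average 2.97 of these fill remaining Coban places (negative binomial shortfall).
- Arm 3 entries after TR Band is full: 72 − 2.97 = 69.0, leaving 31.0 concurrent.

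Simulation with the 50/50 caps, several splits of the 28 places and 50% or 65% diagnostic arrivals gives mean concurrent entries (TR Band still open for the subject's own procedure type) of 27–30 with permuted blocks of 6 and 30–32 with simple randomisation (95% range about 15–57). Subjects without a chance of TR Band therefore average 68–73. Without caps, a 1:1:2 list would give about 41 and 2:2:1 about 83.

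**Overridden draws.** 156 × 2/3 = 104 draws to Arms 1 and 2, less 56 places = 48 Arm 3 subjects whose list assignment was set aside.

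**Bias from a drift of d points with no device effect.**
- Step at the amendment: TR Band mean is 0.72p + 0.28(p + d) = p + 0.28d. Arm 3 mean is p + d. Bias = 0.72d.
- Step when TR Band closes: 70 of 100 Arm 3 subjects are shifted. Bias = 0.70d.
- Straight line over 373 subjects: mean entry position is about (72 × 109 + 28 × 259) ÷ 100 = 151 for TR Band and 0.30 × 259 + 0.70 × 337 = 314 for Arm 3. Bias = (314 − 151) ÷ 373 = 0.44d.

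**Type I error**, summing exact binomial probabilities over outcomes where the pooled two-sample z exceeds 1.96 in size:

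| Drift pattern | Base rate | d = 0 | d = 2 | d = 3 | d = 5 |
|---|---|---|---|---|---|
| Step at amendment | 84% (planned) | 5.1% | 6.0% | 7.3% | 11.9% |
| Step at amendment | 89% (interim: 11% failure) | 5.2% | 6.6% | 8.5% | 15.8% |
| Step at TR Band closure | 84% | 5.1% | 6.0% | 7.1% | 11.0% |
| Straight line | 84% | 5.1% | 5.5% | 5.9% | 7.6% |

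**Power at 84% v 95%, same test.**

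| TR Band v Arm 3 | Power |
|---|---|
| 100 v 100, pooled, no drift | 75% |
| 28 v 28, concurrent, current list | 28% |
| 28 v 15 to 28 v 57, spread of concurrent Arm 3 entries | 7% to 38% |
| 28 v 100, concurrent, new list | 53% |
| 72 v 100 | 70% |

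Downward drift can hide a benefit. With a true 11-point gain, a 3-point fall at the amendment cuts pooled power from 75% to 69% if the fall is equal on the logit scale, or to 48% if it is equal in points. (The 75% is below the plan's stated 80%; that is a separate matter.)

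**The case against.** The protocol discloses all of this: the 72 earlier controls, the remaining places and the redirect rule are in section 3.1. Redirection follows a fixed rule after consent, not operator choice, and nothing in the text shows selective exclusion. No drift is reported, and several features limit it: one centre, operator training by "performing 2 run in procedures prior to enrolling patients in this study", fixed TR Band weaning, fixed diagnostic heparin dosing and the 50/50 caps. Modest drift does modest harm: a straight-line change of 2–3 points leaves type I error at 5.5–5.9%. The 15.8% figure needs TR Band failure to fall from 11% to 6%. The protocol-set gap in total time to hemostasis (about 31 v 120 minutes) could not plausibly come from drift. Coban v TR Band is essentially unaffected, with 72 + 28 in each arm. Finally, about 70 depends on an unstated ratio.

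Most of this stands and it bounds the harm. It does not answer the point. Disclosing how subjects are assigned does not make the assignment random, and stable practice is exactly what randomisation spares the analyst from assuming. Practice is not wholly fixed either: section 1.6 leaves bivalirudin use and post-PCI infusion to the operator. The 72 of 100 holds whatever the list ratio.

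**Conclusion.** The concern holds. Arm 3 v TR Band, as planned, is mostly a comparison across periods. Exactly 72 of 100 controls predate Arm 3, and under a 1:1:1 list 68–73 of 100 Arm 3 subjects on average have no randomised chance of TR Band (43–85 in a single trial with simple randomisation). The randomised core is about 28 v 28, and no planned analysis isolates it.

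The resulting bias is 0.44 to 0.72 of whatever drift occurs. Its size is unknown because the documents report none. The conclusion applies to initial hemostasis and radial artery occlusion in this one comparison. It must be fixed because one of the trial's two comparisons with standard care would otherwise be reported as randomised when most of it is not.

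**What to change.** 1. **Allocation.** For subjects still to be enrolled, replace the old list with a table stratified by diagnostic or PCI, which is known because randomisation follows the procedure. Set the ratio in each stratum by the places left: 28:28:100 overall, or 7:7:25 in each stratum if the 28 places split 14/14. TR Band then stays open to the end. Delete the rule sending screen failures to Arm 3. If TR Band is already full in a stratum, relax the 50/50 cap within the 28 places, or state that Arm 3 subjects there have no concurrent control.
2. **Analysis.** Pre-specify, for initial hemostasis and radial artery occlusion, an Arm 3 v TR Band comparison restricted to subjects randomised while TR Band was open in their stratum, adjusted for procedure type. Classify anyone already redirected from the REDCap draw and audit log. State its power. Whether it is primary or a key sensitivity analysis is the sponsor's choice.
3. **Reporting.** Describe the pooled 100 v 100 result as including non-concurrent, partly non-randomised subjects. The new list alone does not cure this: the 72 early controls still give 0.72d for a step at the amendment, and 0.36d instead of 0.44d for a straight line.

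**Cost.** One allocation table and amendment wording. REDCap is already being changed for the Arm 3 instrument, and the 156 further subjects stay the same. The price is precision, and only if the concurrent analysis is primary: about 53% power with the new list, against 75% pooled. A pre/post-amendment term bridged through Coban does not recover it (about 50–52%). Extra TR Band subjects would: 44 more (72 v 100) gives about 70%, and 72 more (100 v 100) gives 75%.
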